Summary of Significance: There is a high burden of ESRD in the US and most patients undergo time-intensive HD treatment during which interventions could be administered. Replacing passive intradialytic activities with cognitively beneficial activities is a missed opportunity. CT and ET are the only two effective non-pharmacological interventions to preserve executive function, which is supported by our pilot data. The findings from this RCT will provide nephrologists who care for the vulnerable population of HD patients with the first feasible and effective interventions for their patients who are at risk for experiencing executive function decline. Interventions are needed to target the prevention of executive function decline, rather than simply attempting to reverse decline or regain executive function.

Study Procedures

This is a 2 by 2 factorial randomized controlled trial (RCT). We will randomize participants to CT alone, ET alone, both CT+ET, or SC resulting in four arms. Randomization will be achieved through balancing methods over the three stratification factors: study center, sex, and race/ethnicity.

Study Population: Men and women with ESRD and receiving maintenance HD 2-3 times weekly at one of the 13 hemodialysis centers participating in the trial will be eligible. We will only enroll new HD patients, as has been done in other RCTs (89-91) of HD patients. The rationale for enrolling new HD patients are: 1) they will not have already experienced the executive function decline associated with HD; 2) there is a high dementia incidence even within the first year of HD; 3) survival bias is present when studying prevalent HD patients; and 4) we want to intervene before the neurodegenerative process begins.

Inclusion Criteria:

Participants must be:

- Within 3 months to 3 years of initiating HD
- 18 years or older at enrollment
- English-speaking

- Willing to participate in research

Exclusion Criteria:

Patients with the following conditions will not be included in the study:

- Pregnancy
- Angina pectoris
- Chronic lung disease requiring oxygen
- Musculoskeletal conditions that limit mobility
- Upper or lower extremity amputation
- Orthopedic disorders exacerbated by physical activity
- Femoral arteriovenous (AV) access
- Blindness/ Legal blindness
- Hepatitis B infection
- Inability to recognize letters and numbers

In addition to patients with these conditions, patients who are currently incarcerated will be excluded from the study.

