Data will be analyzed according to the intention-to-treat principle. We will test the main effect of CT alone (arm 1) and the main effect of ET alone (arm 2) as well as the interaction between CT+ET (arm 3) compared with SC (arm 4). Baseline characteristics will be compared among treatment groups to test adequacy of randomization and identify possible confounders. If there are concerns about imbalances between treatment groups with respect to important risk factors for executive function decline, we will adjust regression-based models as necessary to account for these differences. Competing events (death or KT) will be quantified; if relevant, sensitivity analysis accounting for competing events will be performed.

1.0. Analytic Methods. Effect of CT, ET, and CT+ET on cognitive outcomes:

Change in executive function between baseline and 3 months will be a continuous outcome. Using a linear regression with the cluster option to account for the centers, we will test the null hypothesis (H01) of no difference in the mean change in executive function in CT alone vs. SC against the alternative hypotheses (HA1) that CT alone has a different mean change in executive function than SC. We will then test the null hypothesis (H02) of no difference in the mean change in executive function in ET vs. SC against the alternative hypotheses (HA2) that ET has a different mean change in executive function than SC.

In addition to these two main effects, we will test the effect of CT depends on ET (interaction). The null hypothesis (H03) is that there is no difference in the mean change in executive function for those in the CT, ET, CT+ET or SC arms vs. the alternative hypothesis (HA3) that at least one of the mean changes in executive function differs.

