H05 Not rejected	Arms 1 and 3 are superior to arm 4, but there is not sufficient evidence to distinguish arm 1 from arm 3; i.e., CT+ET is an effective strategy compared with SC, but we cannot tell if the CT+ET is effective beyond that of CT alone.	There is insufficient evidence to distinguish arm 3 from arm 4 and arm 1 from arm 3; i.e., CT+ET is not an effective strategy compared with SC and no better than CT alone.
H06 Rejected	Arm 2 is superior to arm 4 and arm 3 is superior to arm 2; i.e., both CT+ET and ET alone are effective strategies compared with SC but CT+ET is more effective.	Arm 3 is superior to arm 2, but there is not sufficient evidence to distinguish arm 3 from arm 4; i.e., CT+ET is not effective compared with SC but better than ET alone.
H06	Arms 1 and 3 are superior to arm 4, but there is not sufficient evidence to distinguish arm 1 from arm 3;	There is insufficient evidence to distinguish arm 3 from arm 4 and arm 2 from arm 3; i.e., CT+ET is not an effective

Not rejected	i.e., CT+ET is an effective strategy compared with SC, but we cannot tell if CT+ET is effective beyond CT alone.	strategy compared with SC and no better than ET alone.
--------------	--	--

Power Calculations: We used a Monte-Carlo simulation (1,000 randomly generated datasets) to estimate the power of a 2-by-2 factorial design with linear regression and Huber-White robust standard errors. We powered the RCT to detect a statistically significant difference in the CT+ET group based on a 3-month change in executive function, given the group mean change and SD in the pilot data.

When each arm of the study has 47 participants, we will have 80% power to detect a statistically significant change of 20 seconds between baseline and 3 months comparing the CT+ET arm to the SC arm. We will also have 95% power to detect a statistically significant change of 15 seconds in the CT arm and >99% to detect a statistically significant change of 18 seconds in the ET arm. Therefore, we would need to recruit 200 participants from 16 centers (approximately 13 participants per center). Even if we were to recruit just 22 participants (rather than 47) into each arm of the study, we would still have >80% power to observe statistically significant changes of 15 seconds for the main effects of CT and ET.

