2.1. Time to Event Outcomes: Mortality. To examine the univariate association between study arm and mortality, separate product-limit estimated cumulative incidence curves will be calculated. Next, we will use a Cox proportional hazards model to estimate the association of study arm with time to the development of mortality. Censoring will occur at loss to follow-up or KT. The hazard function for the Cox model is:

$$\lambda(t|X_i) = \lambda_0(t) \exp(X_i \beta)$$

where x_i is the value of the covariate X for the i th participant, and $\lambda_0(t)$ is the baseline hazard function. If the proportional hazards assumption is not met, we will include an interaction with time.

2.2. Dichotomous Outcomes: Poor Lower Extremity Function, poor HRQOL, return to work, and amputation. We will test whether the study arm is associated with poor lower extremity function, poor HRQOL, return to work, and amputation using logistic regression or a modified Poisson regression (145), if the outcome is $>10\%$.

2.3. Count Outcomes: Number of Falls and Hospitalizations. We will use Poisson regression to test whether the study arm is associated with the number of falls and hospitalizations within the 3 months of the intervention.

3.0. Analytic Methods: Effect of CT, ET, and CT+ET on patient-centered outcomes.

Change in Patient-centered Outcome: For each patient-centered outcome, we will calculate a score. We will treat each patient-centered outcome as continuous and will estimate the change in these outcomes between baseline and 3 months. We will analyze each patient-centered outcome separately. We will analyze the change in these outcomes using the analytic plan described in 1.0.

3.1. Change in Patient-centered Outcome over 6 Months. Patient-centered outcomes are longitudinal data (3 and 6 months) and analyzed using the analytic plan described in 2.0 for repeated measures of executive function.

4.0. Treatment Effect Heterogeneity. Frailty has been associated with worse trajectories of executive function in older adults (146) and HD patients (16). Therefore, we will explore treatment heterogeneity between those who are frail and nonfrail in all primary and secondary outcomes. We will include an interaction term between frailty status and intervention type (study arm) to assess difference in treatment effect by frailty status. Using a similar approach, we will test for treatment effect heterogeneity by age, sex, and race/ethnicity.

Risks:

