All participants provided written informed consent and were compensated with \$10 (funding from NIDDK R01DK114074). This trial was approved by the Johns Hopkins Institutional Review Board (IRB00152858) and sIRB with NYU, and reviewed by the Fresenius Medical Care Holdings, Inc. Investigator Initiated Trials Review Committee and DaVita Clinical Research. COVID-19 restrictions in dialysis facilities between 2020-2022 affected recruitment and study operations, leading to the Data and Safety Monitoring Board (DSMB) recommendation of trial termination. Therefore, this trial was terminated on 12/08/2023. The study was registered at [clinicaltrials.gov](https://clinicaltrials.gov/ct2/show/NCT03616535) (NCT03616535).

Eligibility

We recruited English-speaking adult (≥18 years) patients with ESKD who had initiated thrice weekly hemodialysis within 3 months to 3 years (09/2018-06/2022) at 14 dialysis centers in the Baltimore, Maryland area and 1 dialysis center in New York City, New York. We limited the study to participants with 3 months-3 years of hemodialysis to capture a population that had potentially reversible cognitive impairment. Exclusion criteria were: 1) inability to participate in ET without assistance; 2) conditions limiting participation (pregnancy, angina pectoris, chronic lung disease requiring oxygen, musculoskeletal conditions, lower- or upper-extremity amputation, orthopedic disorders exacerbated by physical activity, femoral vascular access, legally blind, inability to recognize numbers and letters as well as hepatitis B infection requiring medical isolation); and 3) incarceration.

Randomization

After the baseline assessment, 121 participants were block-randomized (based on sex, race, and dialysis center, factors chosen to remove their effects on cognition) into 4 arms using a secure computer-based allocation system (R).

Statistical Analysis

Baseline characteristics of participants were presented by arm and compared using ANOVA test for normally distributed continuous variables, Kruskal-Wallis test for nonnormally distributed continuous variables, and Chi-squared test for categorical variables. Differences in the primary and secondary outcomes were tested using these methods as well.

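### Protocol section 1.0: if H03 is run as its written four-arm (3-df) null with the cluster option on 13–18 centres, it rejects in about 7–10% of null trials instead of 5%

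*Combined protocol and SAP*

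**What the plan says.** **Model.** Protocol, Statistical Methods, section 1.0, analyses the 3-month change in executive function "Using a linear regression with the cluster option to account for the centers". It states no small-sample correction or reference distribution. The Power Calculations paragraph mentions Huber-White robust errors without mentioning centres.

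**H03.** It is described in three ways.
- It is introduced as an interaction: "we will test the effect of CT depends on ET (interaction").
- Its null is then written as "there is no difference in the mean change in executive function for those in the CT, ET, CT+ET or SC arms", with the alternative that at least one mean differs (3 df).
- The conclusions that follow, and Table 3, read it as CT+ET (arm 3) against standard care (arm 4).

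**Decision rule.** Table 3 is introduced as applying when H01 and H02 have been rejected. The positive conclusions in the text above it require H01, H02 and H03 all to be rejected.

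**Number of centres.** Study Population says "at one of the 13 hemodialysis centers participating in the trial". Power Calculations says "we would need to recruit 200 participants from 16 centers". The named sites are 10 Fresenius, 4 DaVita and 4 in New York, 18 in all. The updated methods (Eligibility) say "14 dialysis centers in the Baltimore, Maryland area and 1 dialysis center in New York City", 15 in all.

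**Other uses.** Section 3.0 sends the 3-month patient-centered outcomes through the plan in 1.0. Section 4.0 adds interactions of study arm with frailty, age, sex and race/ethnicity and names no variance estimator.

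**Updated methods (Statistical Analysis).** These describe linear regression and ANCOVA adjusted for age, education and the baseline value, and use ANOVA or Kruskal-Wallis for differences across arms. They do not mention a cluster option, centre adjustment or subgroup interactions.

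**The concern.** A cluster-robust variance is estimated from as many independent pieces as there are clusters. For a single coefficient, 13–18 clusters with a t reference on G−1 degrees of freedom is usually tolerable. For a joint test, a 3×3 covariance matrix has to be estimated and inverted from those few pieces, and the usual F(3, G−1) reference does not fully allow for that, so the test rejects too often. This is a matter of the error rate, not of power.

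At stake is any p-value quoted for H03 as a four-arm comparison, the same test repeated over the patient-centered outcomes, and the multi-df subgroup interactions if they are fitted in the same model. Participants are randomised individually within centre, so clustering is not needed for a valid test of no effect.

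**Working it through.** **The plan's own figures.** The documents state no false-positive rate beyond the two-sided 0.05 in the updated methods. The sample size reproduces: 4 × 47 = 188, and 188 / (1 − 0.06) = 200. The 80% power figure cannot be reproduced because no SD is given; the point does not depend on it.

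**Inputs from the documents.** G = 13, 15, 16 or 18 centres; 188 evaluable or 200 recruited; 121 randomised at 15 centres; 121 − 25 interrupted follow-ups = 96 as a low case; four equal arms in blocks of four within centre, sex and race/ethnicity.

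**Assumptions, not in the documents.** Centre intraclass correlation 0–0.05; centre sizes equal, moderately unequal (about 1:4) or strongly skewed (about 1:16); frailty prevalence 35–40%; three race/ethnicity levels; the usual scalar factor G/(G−1) × (N−1)/(N−K) with an F(q, G−1) reference.

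**Step 1: equal centres, by formula.** The cluster Wald statistic divided by q behaves as a Hotelling statistic, (G−1)/(G−q) × F(q, G−q). With c the 5% point of F(3, G−1), the true size is P[F(3, G−3) > c(G−3)/(G−1)].

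| G | c | c(G−3)/(G−1) | True size |
|---|---|---|---|
| 13 | 3.490 | 2.909 | 8.7% |
| 15 | 3.344 | 2.866 | 8.1% |
| 16 | 3.287 | 2.849 | 7.8% |
| 18 | 3.197 | 2.821 | 7.5% |

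**Step 2: simulation with no effect in any arm** (5,000 runs, intraclass correlation 0.02; Monte Carlo standard error about 0.4 points near 8%). Rejection rates in %:

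| N, G | Centre sizes | H01 (1 df) | CT×ET (1 df) | Four-arm, clustered | Four-arm, centre indicators |
|---|---|---|---|---|---|
| 200, 13 | equal | 4.6 | 4.2 | 8.2 | 4.7 |
| 200, 13 | moderate | 4.8 | 4.8 | 9.6 | 4.6 |
| 200, 13 | skewed | 7.1 | 6.5 | 14.8 | 5.3 |
| 200, 16 | equal | 5.0 | 4.8 | 8.3 | 4.7 |
| 200, 16 | moderate | 4.8 | 5.3 | 8.8 | 4.9 |
| 200, 18 | equal | 4.9 | 5.0 | 7.8 | 5.1 |
| 200, 18 | moderate | 5.7 | 5.4 | 8.6 | 5.2 |
| 200, 18 | skewed | 6.0 | 5.9 | 11.6 | 4.8 |
| 121, 15 | moderate | 5.5 | 5.1 | 9.4 | 5.1 |
| 121, 15 | skewed | 6.5 | 6.6 | 13.1 | 4.9 |
| 96, 15 | moderate | 5.6 | 5.0 | 9.9 | 5.1 |
| 96, 15 | skewed | 5.9 | 6.4 | 12.8 | 5.2 |

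Over all settings tried, including 188 participants with intraclass correlation 0 and 0.05, the clustered four-arm test rejected in 7.1–9.7% (equal), 7.7–10.1% (moderate) and 11.2–15.5% (skewed). A second way of generating very unequal centres gave 11.3–14.1%. CT+ET versus standard care alone gave 4.7–6.8%.

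**Step 3: the decision rule.** In null simulations with 13, 16 and 15 centres (188, 188 and 96 participants), H01 and H02 were both rejected in 0.8–1.3% of trials, and H01, H02 and H03 all together in 0.5–1.2%.

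**Step 4: section 4.0, if the same clustered model were used.** Arm by frailty rejected in 7.6–16.4% and arm by sex in 7.5–14.0%, about the same as H03. Arm by age gave 9.0–18.0%. Arm by a three-level race/ethnicity factor (6 df) was far worse: 16–24% by the equal-centre formula and from 18% to about 60% in simulation, depending on level frequencies and centre sizes.

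**The case against.** The strongest objection is that the inflated test triggers no conclusion by itself. A reader might infer that 8–14% of null trials would wrongly declare CT+ET effective, because Table 3 turns on H03. The documents do not support that: Table 3 is conditional on H01 and H02, and step 3 puts the joint false rejection at about 1%. Where CT or ET truly differs from standard care, the four-arm null is false and its size is not the relevant error. This objection stands and confines the harm to the stand-alone H03 p-value and its repeats under section 3.0.

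Second, the updated methods may have superseded the cluster option. They give plain linear regression and send the four-arm comparison to ANOVA or Kruskal-Wallis, where the rate is about 5%. This also stands, but only conditionally: the update does not say the option was withdrawn, and its list of adjusters omits centre.

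Third, H03 may be meant as a 1-df test, in which case the inflation is slight. That is so, but the null and alternative actually written are the four-arm version.

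Fourth, the protocol plans about 13 participants per centre, so strong skew is not established. That is accepted; the upper range is labelled as an assumption.

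A reader might also infer that every section 4.0 test is worse than H03. Frailty and sex are not, section 4.0 does not say it uses this model, and its tests are exploratory.

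**Conclusion.** The point holds for protocol section 1.0 as written, and conditionally. With the four-arm null, the cluster option and 13–18 centres, the 5% test has a true size of about 7–10% with equal or moderately unequal centres. With strongly skewed centres it is about 11–14%, and 15.5% in the most extreme setting tried. Even the most favourable case, equal centres, gives 7.5–8.7% by formula.

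H01, H02 and the 1-df versions of H03 are not materially affected (about 4–7%). The inflation does not carry through to the Table 3 verdicts, and it vanishes if clustering was dropped in the final analysis. The result rests on the assumed intraclass correlation, on the centre-size pattern and on the usual software reference distribution; a chi-square reference would be worse (11.9–15.5% with equal centres).

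**What to change.** - In section 1.0, replace the cluster option with centre indicators, since centre is already a randomisation stratum. Use ordinary or HC3 standard errors and residual degrees of freedom, and use the same model for every multi-df arm test in sections 3.0 and 4.0. Centre indicators gave 4.6–5.7% in the simulations. With the CT+ET arm SD set 1.7 times larger, they gave 5–6% with ordinary errors, and HC3 errors gave about 5%.
- Define H03 as one test consistent with its use in Table 3 (arm 3 versus arm 4, 1 df). Name the CT by ET interaction and any four-arm test separately.
- State in the updated methods whether clustering was kept. Do not report a multi-df p-value from an uncorrected cluster F test.
- If clustering is kept, use a small-sample method built for joint tests (CR2 with a Satterthwaite-type reference, or a wild cluster bootstrap). Changing the reference to Hotelling alone is not enough under strong skew, where it still gave 8.1–10.4%.

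Cost: a change of wording, one re-run, 12–17 degrees of freedom (G−1 for 13–18 centres) out of 96–188 participants, and somewhat larger p-values for H03 and the interactions.

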From this model, we will use linear combination methods to test H04 (no difference in mean change in executive function for arm 1 vs. 2) vs. HA4 (arm 1 has a different mean change in executive function than arm 2). We will then test H05 (no difference in mean change in executive function for arm 1 vs. 3) vs. HA5 (arm 1 has a different mean change in executive function than arm 3). We will test H06 (no difference in mean change in executive function for arm 2 vs. 3) vs. HA6 (arm 2 has a different mean change in executive function than arm 3). If H01 is not rejected, we will conclude that there is insufficient evidence that arm 1 is more effective than arm 4 in preserving executive function. If H02 is not rejected, we will conclude that there is insufficient evidence that arm 2 is more effective than arm 4 in preserving executive function. If H03 is not rejected, we will conclude that there is insufficient evidence that arm 3 is more effective than arm 4.

If H01, H02, and H03 are rejected, but H04 is not rejected, we will conclude that arms 1 and 2 are more effective than arm 4, but there is no difference in the effectiveness of arms 1 and 2. Similarly, if H01, H02, and H03 are rejected, but H05 is not rejected, we will conclude that arms 1 and 3 are more effective than arm 4, but there is no difference in the effectiveness of arms 1 and 3. And finally, if H01, H02, and H03 are rejected, but H06 is not rejected, we will conclude that arms 2 and 3 are more effective than arm 4, but there is no difference in the effectiveness of arms 2 and 3. The following table below details the conclusions we will draw based on hypotheses testing if H01 and H02 are rejected:

Table 3: Hypothesis Testing for the Primary Outcome

Table 3: Hypothesis Testing for the Primary Outcome		
	H03 rejected	H03 not rejected
H05 Rejected	Arm 1 is superior to arm 4 and arm 3 is superior to arm 1; i.e., both CT+ET and CT alone are effective strategies compared with SC but CT+ET is more effective.	Arm 3 is superior to arm 1, but there is not sufficient evidence to distinguish arm 3 from arm 4; i.e., CT+ET is not effective compared with SC but better than CT alone.

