For CT, ET and CT+ET arms, we evaluated each participant's adherence to the assigned intervention as: the number of dialysis sessions that the participant attended and participated in the intervention/the number of dialysis sessions that the participant attended)*100%.

The effect of interventions was analyzed according to the intention-to-treat principle. Changes in executive function, global cognitive function, ESKD-specific clinical outcomes, and patient-centered outcomes between baseline and 3 months were handled as continuous outcomes. After visually verifying the linearity, normality, and equal variance assumption, we used linear regression to test the main effect of CT alone and the main effect of ET alone as well as the interaction between CT+ET compared with SC; we also tested these effects with an ANCOVA analysis. In addition, we tested whether the impact of CT, ET, and CT+ET differed from each other. The main comparison used models adjusted for age at enrollment, education, and baseline measures of outcomes, which were adapted to account for imbalances between groups with respect to important risk factors for the outcomes.

All analyses were performed using Stata 16.1 (StataCorp, College Station, TX). Statistical significance was defined as a two-sided p-value <0.05. There was no missingness in adjusted covariates.

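### H03 is defined as three different tests, none of the listed hypotheses is CT+ET versus SC, and the stated decision rule can misjudge the combined arm in either direction

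*Combined protocol and SAP*

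**What the plan says.** The primary objective (Objectives) compares CT, ET and CT+ET each with SC. Power Calculations sizes the trial on the combined arm: "When each arm of the study has 47 participants, we will have 80% power to detect a statistically significant change of 20 seconds", "comparing the CT+ET arm to the SC arm".

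Section 1.0 sets H01 (arm 1 v 4) and H02 (arm 2 v 4), then introduces the third hypothesis: "we will test the effect of CT depends on ET (interaction). The null hypothesis (H03) is that there is no difference in the mean change". The sentence goes on to name all four arms, and the alternative is that at least one mean differs. H04, H05 and H06 are arms 1 v 2, 1 v 3 and 2 v 3.

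The decision rule reads H03 in a third way: "If H03 is not rejected, we will conclude that there is insufficient evidence that arm 3 is more effective than arm 4". Table 3, which applies when H01 and H02 are both rejected, uses that reading throughout. With H03 and H05 both not rejected, it concludes "CT+ET is not an effective strategy compared with SC and no better than CT alone". With H03 rejected and H06 (arm 2 v 3) not rejected, it concludes "i.e., CT+ET is an effective strategy compared with SC, but we cannot tell if CT+ET is effective beyond CT alone".

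The Statistical Analysis part of the updated methods tests the two main effects "as well as the interaction between CT+ET compared with SC", and adds comparisons of the three active arms with each other. It does not restate or withdraw H01 to H06 or Table 3.

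**The concern.** An interaction, a four-arm omnibus test and a two-arm contrast answer different questions. The interaction asks whether the joint effect departs from the sum of the separate effects. The omnibus asks whether any arm differs. Only the contrast of arm 3 with arm 4 asks whether CT+ET works.

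If H03 is run as the interaction, perfectly additive benefits lead to the conclusion that CT+ET has not been shown effective. If it is run as the omnibus, a benefit confined to CT or ET alone leads to the conclusion that CT+ET is effective. The arm that set the sample size could therefore be misreported, in a direction that depends on which version the analyst picks.

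Two smaller faults sit in the same rules. The H06 row of Table 3 draws a conclusion about arms 1 and 3 in a cell that tests arms 2 and 3. The text also turns non-rejection of H04 to H06 into a finding that the arms are equally effective.

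**Working it through.** **Algebra.** Let the mean change be b0 + bCT·CT + bET·ET + bX·CT·ET, with SC as reference.

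| Test | Quantity | Listed as |
|---|---|---|
| arm 1 v 4 | bCT | H01 |
| arm 2 v 4 | bET | H02 |
| arm 1 v 2 | bCT − bET | H04 |
| arm 1 v 3 | bET + bX | H05 |
| arm 2 v 3 | bCT + bX | H06 |
| arm 3 v 4 | bCT + bET + bX | none |
| interaction | bX | H03 as introduced |
| four-arm omnibus | bCT = bET = bX = 0 | H03 as its null is written |

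Arm 3 v 4 is the only one of the six pairs without a hypothesis, yet it is how H03 is interpreted.

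**Inputs.** From Power Calculations: 47 per arm; 20 s for CT+ET at 80% power, 15 s for CT at 95%, 18 s for ET above 99%. From the updated methods: "Statistical significance was defined as a two-sided p-value <0.05". No SD is given, so the stated 80% cannot be checked independently; the SD has to be back-solved and is an assumption.

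**Implied SD.**
- If the 80% refers to arm 3 v 4: SD = 20·√(47/2)/(1.960 + 0.842) = 34.6 s.
- If it refers to the interaction, whose standard error is 2·SD/√47: SD = 20·√47/(2 × 2.802) = 24.5 s.
- CT at 15 s and 95%, as arm 1 v 4: SD = 15·√(47/2)/(1.960 + 1.645) = 20.2 s.

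The range 20.2 to 34.6 s is carried through.

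**By formula at SD 34.6.** The standard error of arm 3 v 4 is 34.6·√(2/47) = 7.14 s; that of the interaction is 2 × 34.6/√47 = 10.09 s.
- Additive truth, 15/15/30 s: arm 3 v 4 has power Φ(30/7.14 − 1.96) = 98.8%. The interaction is 30 − 15 − 15 = 0, so it is rejected in 5%.
- 15/18/20 s: arm 3 v 4 has power 80%. The interaction is 20 − 15 − 18 = −13 s, with power Φ(13/10.09 − 1.96) = 25%.
- 15/18/0 s (the combination does nothing): the interaction is −33 s, rejected in Φ(33/10.09 − 1.96) = 90%. Every cell of Table 3 with H03 rejected then credits CT+ET.

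**By simulation.** Four normal arms, equal SD, no clustering, t tests and the 3-df F test, at least 40,000 trials per scenario. A significant arm 3 v 4 result means significant in favour of CT+ET. Percentages are of all trials, 47 per arm.

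| SD (s) | 15/15/30: 3 v 4 significant, interaction not | 15/18/20: same | 15/18/0: omnibus rejected, no significant 3 v 4 benefit |
|---|---|---|---|
| 20.2 | 95% | 41% | 97% |
| 24.5 | 95% | 55% | 96% |
| 34.6 | 94% | 60% | 77% |

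Table 3 applies only when H01 and H02 are both rejected. At SD 34.6 the first two columns then cover 36% and 24% of all trials. Because those two hypotheses are both rejected in only about 39% and 46% of trials, that is about 94% and 52% of the trials that reach the table. The third column is about 93% of the trials that reach it.

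With 121 randomised (121/4 ≈ 30 per arm), the first column is 87% to 95% over the same SD range.

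**Table 3 against itself.** In the cell with H05 rejected and H03 not rejected, the table ranks arm 3 above arm 1. The table's own condition (H01 rejected) puts arm 1 above arm 4. The cell nevertheless calls CT+ET ineffective against SC.

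**The case against.** The authors very probably meant arm 3 v 4. The decision rules, the power statement and the primary objective all point there, and section 1.0 already takes linear combinations from the fitted model, so the contrast is one command away. This is a fair account of intent, but neither document specifies the contrast, and both written versions of H03 are something else.

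The false negative belongs to the interaction reading. Under the omnibus null as literally written, H03 goes unrejected in at most 3.7% of trials that reject H01 and H02 (additive effects or 15/18/20 s, 47 per arm). That stands. Under the omnibus the main risk is false credit to CT+ET, and the scenario showing it (15/18/0 s) is hypothetical and runs against the protocol's premise that the combination beats either component.

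The explicit verdict of ineffectiveness appears only in Table 3, which is conditional, so the 36% and 24% are the right figures for that wording. The rule in the text, which concludes insufficient evidence, carries no such condition, so the 94% and 60% apply to it.

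The SD of 34.6 s is chosen by assuming the 80% is for arm 3 v 4, and it gives only Φ(15/7.14 − 1.96) = 56% for CT at 15 s against the stated 95%. If the 80% refers to the interaction, the 20 s may be the interaction itself and 15/18/20 may not be the planned arm effects. This is a real limit on the middle column; the additive result barely moves with SD.

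The updated methods do not restate Table 3, and the trial has ended, so whether its verdicts still govern is unclear. That makes the remedy one of clarification and reporting; it does not remove the ambiguity.

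**Conclusion.** The concern holds. H03 carries three incompatible meanings, the powered comparison has no hypothesis of its own, and the update leaves this unresolved. Run as the interaction, the rule misses a combined benefit that the direct contrast detects in about 94% to 95% of trials under additivity, and in 41% to 60% with effects of 15/18/20 s. Run as the omnibus, it credits an ineffective combination in about 77% to 97% of trials when CT and ET work alone. The sizes rest on assumed SDs of 20.2 to 34.6 s, 47 per arm, equal variances and no clustering; the inconsistency itself rests on the text alone. It must be fixed because it decides the primary conclusion on the arm that set the sample size.

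**What to change.** - Redefine H03 as no difference in mean change between arms 3 and 4, tested as bCT + bET + bX from the same model, and report the estimate with its 95% CI.
- List the interaction bX as a separate hypothesis (H07), and any omnibus test separately too. Neither should bear on whether CT+ET is effective.
- Rewrite Table 3 on the arm 3 v 4 estimate, its sign and its CI, since the alternatives are two-sided but the conclusions claim superiority. Remove the contradictory cell and correct the H06 row to arms 2 and 3.
- Where H04 to H06 are not rejected, say that the arms were not distinguished and give the CI.
- Correct the matching sentence in the updated Statistical Analysis, and state in any report which contrast each CT+ET result represents.

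The cost is a wording change and one linear-combination command on a model already fitted. No new data are needed.
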